## 9.6 Objective and subjective sleep continuity

Mean values are the mean of the two PSG treatment nights at each visit.

Absolute change from Baseline to Days 1 and 2 in mean number of shifts from S2, SWS or REM to S1 or wake for the whole night will be summarized. Absolute values will also be summarized.

Absolute change from Baseline to Days 1 and 2 in mean wake time during sleep (defined as the time [min] spent in epochs scored as wake between LPS and last epoch not scored wake) for the whole night will be summarized. Absolute values will also be summarized.

Absolute change from Baseline to Days 1 and 2 in mean number of awakenings (defined as the number of awakenings between first epoch and last epoch not scored wake) will be summarized for the whole night, for each quarter of the night, and for each hour of the night. Absolute values will also be summarized.

Absolute change from Baseline to Days 1 and 2 in the mean self-reported number of awakenings will be summarized. Absolute values will also be summarized.

## 9.7 Sleep efficiency

Sleep efficiency (%) is defined as  $100 \times (\text{TST [min]} / \text{total time in bed [min]})$  where total time in bed is fixed to 480 min during the PSG nights.

Absolute change from Baseline to Days 1 and 2 in Sleep efficiency will be summarized. Absolute values will also be summarized.

## 9.8 Insomnia severity

The Insomnia Severity Index (ISI®) is a validated instrument to quantify perceived insomnia severity [Bastien 2001]. The ISI is composed of seven items that evaluate (1) severity of sleep-onset (initial), (2) sleep maintenance (middle), (3) early morning awaking (terminal) problems, (4) satisfaction with current sleep pattern, (5) interference with daily functioning, (6) noticeability of impairment attributed to the sleep problem, and (7) level of distress caused by the sleep problem. Each item is scored as 0 (not at all), 1, 2, 3 or 4 (extremely) and the time interval considered is the last 2 weeks. Total scores range from 0–28 with high scores indicating greater insomnia.

Absolute values at screening (V1) will be summarized.

## 9.9 Next-day performance

Daytime alertness and daytime ability to function are to be assessed once per treatment period (i.e., on the second PSG evening). Morning sleepiness is to be assessed twice per treatment period (i.e., on the first and second PSG evening).

Absolute change from Baseline to Days 1 and 2 in next-day performance assessed by scores on the VAS (mm) assessing morning sleepiness, daytime alertness and daytime ability to function. Absolute values will also be summarized.

## 10 SAFETY ANALYSIS

Unless noted otherwise, the SS will be used for summaries and listings of safety data.

All safety data will be listed.

### 10.1 Adverse events

Adverse events (AEs) will be coded using MedDRA. The MedDRA version used for reporting will be specified in the footnote of the applicable output.

AEs will be assigned to the dose group based on the AE start date. AEs with an incomplete or missing start date will not be assigned to a treatment period.

Treatment-emergent AEs are those that occurred from the start of the treatment period [see Section 13.1] until 5 days after last study treatment intake in each treatment period (or until the start of the next treatment period, if earlier).

Non-treatment emergent AEs are those that occurred before the first treatment period or more than 5 days after the last study treatment intake of a given treatment period until the start of the next treatment period, or until the end of the last treatment period [see Section 13.2].

Post-treatment emergent AEs are those that occurred after the end of the last treatment period [see Section 13.2].

AEs will be summarized (frequency counts and percentages) by SOC and/or PT, and maximum intensity. AEs occurring during the run-in single-blind placebo treatment period will also be included in AE summaries defined below (except for AEs leading to premature discontinuation or temporary interruption, or on-treatment deaths).

Deaths (whether on-treatment or not), and AEs (whether treatment-emergent or not) leading to premature study treatment discontinuation or temporary interruption will be assigned to the dose group (including single-blind placebo) of the last dose taken before death or onset of AE, respectively.

The following AE summaries will be provided:

- Treatment-emergent AEs,

- Treatment- and non-treatment emergent AEs,
- Post-treatment emergent AEs,
- Treatment-emergent AEs related to study treatment,
- Treatment- and non-treatment emergent AEs related to study treatment,
- AEs leading to premature discontinuation of double-blind study treatment,
- AEs leading to temporary interruption of double-blind study treatment,
- Occurrence of treatment and non-treatment emergent non-serious AEs,
- Treatment-emergent serious AEs (SAEs),
- Treatment- and non-treatment emergent SAEs,
- Occurrence of treatment- and non-treatment emergent SAEs,
- Treatment-emergent SAEs related to study treatment,
- Treatment- and non-treatment emergent SAEs related to study treatment,
- Treatment- and non-treatment emergent AEs with fatal outcome,
- Treatment- and non-treatment emergent AEs related to study treatment with fatal outcome,
- Deaths with cause of death.

All AEs will be listed as well as all deaths with cause of death. In addition, separate listings will be provided for AEs leading to discontinuation of double-blind study treatment, and SAEs.

Treatment-emergent AEs of special interest (AESI) both according to investigator (based on the question ‘Do you consider this AE an Adverse Event of Special Interest (AESI)?’ recorded as ‘Yes’ on the ‘Adverse Event’ page), and after adjudication by an Independent Safety Board (ISB), will be summarized. The following summaries will be provided:

- Treatment- and non-treatment emergent AESI as per investigator,
- Treatment- and non-treatment emergent AESI after ISB adjudication.

AESI will be listed separately.

A subject with multiple intensities reported for an AE will be summarized under the maximum intensity recorded for the event. A subject with multiple occurrences of an AE is counted only once in the AE category (e.g., SOC, PT).

An incomplete (day or month missing) or missing AE date will be imputed as described in the [Table 2](#) below. The ‘upper limit’ refers to the latest possible date.

As an example: If AE resolution date is MAR2017 (day missing), the upper limit is 31MAR2017. If AE resolution date is 2017 (day and month missing), the upper limit is 31DEC2017.

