10.2.4.1 Adverse events

An AE is defined as any event that is recorded on the AE eCRF module regardless of the onset date.

TEAEs for a given treatment group are those with onset date/time \geq start date/time of double-blind study treatment of each treatment period and \leq 5 days after end of study treatment of each treatment period, and \leq 5 days after study treatment discontinuation. AE, including AEs of special interest [see Section 6.2], with onset prior to study treatment dose that worsened during the treatment phase will also be reported as TEAEs.

The handling of missing or incomplete dates/time of AEs and assessments will be described in the SAP.

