10.3.5 Analysis of the safety variables

All safety analyses will be performed on the SS, by dose, using descriptive statistics. All safety data will be listed, with flags for quantitative abnormalities.

Observations and assessments (e.g., AEs, laboratory data) occurring within a treatment period (from the time of dosing to the time immediately prior to the next dose) will be assigned to the dose taken in that period.

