## **12 CHANGES OR CLARIFICATIONS TO ANALYSES PLANNED IN THE STUDY PROTOCOL**

### **12.1 Changes to the analyses planned in the study protocol**

Analyses of secondary and exploratory efficacy endpoints will be based on the FAS (a broader analysis set) instead of the modified FAS which is linked only to the primary endpoint by requiring at least one WASO assessment at baseline and one at Days 1 and 2 of any given treatment period.

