## **13 GENERAL DEFINITIONS AND DERIVATIONS**

### **13.1 Treatment start and end dates**

Double-blind study treatment start and end dates are the earliest and latest dates, respectively, of dose intake recorded on the ‘Study Double-blind Treatment Log’ page.

Run-in single-blind placebo treatment start date (i.e., the start date of the single-blind placebo treatment period), is the earliest date of dose intake (i.e., date of capsules administered) recorded on the ‘Study Single Blind Treatment Dispensing & Accountability’ page at V2.

Treatment period 1 start date is the earliest date of dose intake (i.e., date of capsules administered) recorded for Visit 3 on the ‘Study Double Blind Treatment Dispensing & Accountability’ page.

Treatment period 2 start date is the earliest date of dose intake (i.e., date of capsules administered) recorded for Visit 4 on the ‘Study Double Blind Treatment Dispensing & Accountability’ page.

Treatment period 3 start date is the earliest date of dose intake (i.e., date of capsules administered) recorded for Visit 5 on the ‘Study Double Blind Treatment Dispensing & Accountability’ page.

Treatment period 4 start date is the earliest date of dose intake (i.e., date of capsules administered) recorded for Visit 6 on the ‘Study Double Blind Treatment Dispensing & Accountability’ page.

Treatment period 5 start date is the earliest date of dose intake (i.e., date of capsules administered) recorded for Visit 7 on the ‘Study Double Blind Treatment Dispensing & Accountability’ page.

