### **13.2 Treatment period**

A treatment period is defined as the time from the start of the treatment period [see Section 13.1] until the start of the next treatment period. The end of the last treatment period (e.g., the fifth treatment period or an earlier treatment period if subject prematurely discontinued) is the date of first safety follow-up telephone call, or 12 days after the last study treatment intake, whichever is earlier.

After the single-blind placebo treatment period, subjects are to receive one of 5 study treatments in each of the 5 double-blind treatment periods in order of the sequence they are randomized to.

These treatment periods are used to assign assessments/events to dose groups (including single-blind placebo).

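### The AESI endpoint runs to end of study, but AE recording and the SAP's AESI tables stop earlier; a minor second point is the undeclared date-only rule for assigning AEs to dose

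*SAP*

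**What the plan says.** **AESI window.** Protocol 6.2 counts AESIs that start or worsen after the first dose of the first treatment period, up to end of study (EOS). Protocol 3.1.1.2 defines EOS as the date of the 30-day call, and Protocol 7.1 places that call 30 (+7) days after last intake. Protocol 9.1.4 and footnote 5 of Protocol Table 3 require AEs to be recorded up to 5 days after discontinuation; Protocol 9.2.2 takes SAEs to day 30. No separate recording rule is given for AESIs. Protocol 10.2.4 says the safety analysis takes in data collected to day 30.

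The AESI lead-in sentence in SAP 10.1 speaks of treatment-emergent events, but its two planned tables cover treatment-emergent and non-treatment-emergent events. The second class closes with the last treatment period, whose end, under SAP 13.2, "is the date of first safety follow-up telephone call, or 12 days after the last study treatment intake, whichever is earlier". Later events are post-treatment emergent, and no AESI table is planned for them.

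**Assignment to dose.** SAP 10.1: "AEs will be assigned to the dose group based on the AE start date". SAP 13.1: "Treatment period 1 start date is the earliest date of dose intake", with the same wording for periods 2 to 5. SAP 10.1 has a different rule for deaths and for AEs leading to discontinuation or interruption, which go to the dose group "of the last dose taken before death or onset of AE".

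Protocol 10.2.4.1 works with clock time: "TEAEs for a given treatment group are those with onset date/time" at or after the start date/time of treatment in the period. Earlier AEs enter only through its worsening clause, under which AEs "with onset prior to study treatment dose that worsened during the treatment phase will also be reported as TEAEs". Protocol 10.3.5 assigns observations over the span "from the time of dosing to the time immediately prior to the next dose". Protocol 6.2 and 9.1.1, however, define TEAEs by day, starting on Day 1.

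SAP 12.1 declares one change only: "Analyses of secondary and exploratory efficacy endpoints will be based on the FAS (a broader analysis set) instead of the modified FAS". SAP 12.3 reports no clarifications.

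**The concern.** AESIs are the named risks of this drug class: narcolepsy-like events, complex sleep behaviours, and suicidal thoughts or behaviours. Protocol 1.3.1 makes safety part of the choice of dose for later trials. If the endpoint window, the recording rule and the tables disagree, an empty late window could be read as absence of events when nobody was obliged to record them. Two programmers could also both follow the documents and produce different AESI tables.

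On assignment, dosing is in the evening, so most of a first dosing date precedes the dose. Protocol 7.2 schedules physical examination, vital signs, blood sampling and AE recording that evening before intake. SAP 10.2 takes that evening's blood sample as the baseline for the dose that follows. A pre-dose abnormality could thus be baseline in the laboratory table and, if reported as an AE starting that day, a TEAE of the dose not yet taken. The two assignment rules in SAP 10.1 could also put such an event in different columns of different tables, though only in rare same-day cases.

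**Working it through.** 1. **Calendar check.** Five periods of 2 nights plus four washouts of 5 to 12 days give 5×2 + 4×5 = 30 and 5×2 + 4×12 = 58 days. This reproduces the 30 to 58 days in Protocol 3.1.2.

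2. **End of the AESI window**, in days after last intake. EOS is at day 30 to 30 + 7 = 37. The first call is at day 5 to 5 + 7 = 12 (Protocol 7.1), so the last SAP period ends between day 5 and day 12.

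| | EOS at day 30 | EOS at day 37 |
|---|---|---|
| Non-serious AESIs, no recording requirement | 30 − 5 = 25 days | 37 − 5 = 32 days |
| Serious AESIs, beyond the day-30 rule | 30 − 30 = 0 days | 37 − 30 = 7 days |
| Outside AESI tables, last period ends day 12 | 30 − 12 = 18 days | 37 − 12 = 25 days |
| Outside AESI tables, last period ends day 5 | 30 − 5 = 25 days | 37 − 5 = 32 days |

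 Protocol Table 3 counts the calls from end of treatment rather than last intake, which moves these figures by no more than a day.

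3. **Start of the AESI window.** The non-treatment-emergent class in SAP 10.1 includes events before the first treatment period. The endpoint in Protocol 6.2 starts only after the first dose, so the tables are also too wide at the front.

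4. **Pre-dose hours on a first dosing date.** Usual bedtime is 21:30 to 00:30 (inclusion criterion 10), first lights-off is within 30 minutes of it, and the dose is about 30 minutes earlier. Ignoring the 5-minute tolerances, doses fall between 20:30 and 00:30. For doses before midnight, 20.5 to just under 24 hours of that date precede the dose; for doses at or after midnight, 0 to 0.5 hours.

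5. **What the date rule does.** With the shortest washout, doses fall on days 1 and 2, the 5-day TEAE window ends on day 7, and the next first dose is on day 8. An onset on day 8 before the dose is a TEAE of neither dose by clock time, but a TEAE of the new dose under the SAP.

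6. **Effect on comparisons.** Assume 10 subjects per sequence, all completing and all dosed before midnight. In the TEAE tables each of the five columns gains 5×10 = 50 pre-dose subject-days. In the combined treatment- and non-treatment-emergent tables each column gains 50 and passes 4×10 = 40 to the next dose, because each treatment stands in period 5 in exactly one sequence. The net is +10 in all five. With a constant background rate, the expected change in any dose-placebo difference is 0.

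7. **Residual drug.** In the shortest cycle the next first dosing date begins 120 to 123.5 hours after the previous last dose. With the 9.9 h half-life in Protocol 3.2, that is 120/9.9 = 12.1 to 123.5/9.9 = 12.5 half-lives.

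**The case against.** **AESI window.** A reader might infer that late AESIs are lost. The documents do not support that. The AE row of Protocol Table 3 is marked at both follow-up calls. Protocol 9.1.4 sets what must be recorded and does not forbid later entries. Protocol 10.2.4.1 counts anything on the AE form regardless of onset date. SAP 10.1 lists AESIs with no window limit and has a general post-treatment AE table. Nor are serious events after day 30 beyond reach: Protocol 9.2.4 keeps them reportable if the investigator considers them related. Drug-attributable risk is probably low more than 12 half-lives after the last dose. What stands is the mismatch: the required recording and the AESI tables do not span the endpoint.

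**Assignment.** A reader might infer that the SAP contradicts the protocol outright, or that the date rule lengthens the TEAE window by about a sixth (7 dates = 168 h against 24 + 120 = 144 h). Neither holds without qualification. The SAP follows the day-based wording of Protocol 6.2 and 9.1.1, against which the excess is zero; the 144 h exists only if 5 days is read as 120 h. Protocol section 10 leaves derivation algorithms to the SAP. Neither document confirms that AE onset time is collected, and SAP Table 2 deals with dates only. Protocol 9.1.2 already gives an AE that worsens after the start of treatment a new line with its own onset date. What stands is that the protocol contains two rules and the SAP uses one without declaring it.

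**Conclusion.** The AESI point holds and is the main one. Followed as written, the plan yields an AESI summary that does not match its endpoint: 25 to 32 days without a recording requirement for non-serious AESIs, and 18 to 32 days outside the AESI tables. This is a gap in definition and completeness, not evidence of missed harm. The figures rest on the call windows of Protocol 7.1.

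The assignment point is minor. Individual events can be credited to a dose not yet taken, and every column including placebo can be slightly inflated. A reader might infer a distorted dose comparison; the balance of the Latin square does not support that under a constant background rate and complete follow-up. The order of treatments would matter only if an earlier dose still caused AEs about 5 or more days after intake. The number of events affected cannot be derived from the documents. Efficacy is untouched by either point.

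**What to change.** **AESI window.** Reconcile Protocol 6.2, 9.1.4 and Table 3 footnote 5 with SAP 10.1 in one of two ways:
- require AESIs to be recorded through the existing 30-day call and add a post-treatment AESI table; or
- restate the endpoint window to match what is collected.

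In either case make the SAP lead-in sentence and its two AESI bullets name the same window, with the same start as the endpoint. The cost is wording plus one table, or wording alone if the window is restated. The call and the AE form exist, and no visit is added.

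**Assignment.** If AE onset time is collected, assign by onset date/time against the recorded time of first dose in each period. Same-day pre-dose onsets then stay with the previous period (run-in for period 1), and worsening is handled by the new onset line under Protocol 9.1.2. If onset time is not collected, keep the date rule and flag onsets on first dosing dates in the AE listing. Declare whichever rule is used in SAP section 12. The cost is SAP wording and some programming; dose time is already in the eCRF (Protocol 5.1.2). Without onset time it is a listing flag and one line of text.

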#### **4 GENERAL ANALYSIS CONSIDERATIONS**

Unless noted otherwise, all statistical summaries will be presented by dose group and in the following order: Placebo, ACT-541468 5 mg, ACT-541468 10 mg, ACT-541468 25 mg, ACT-541468 50 mg.

Categorical data will be summarized by frequency counts and percentages. Unless specified otherwise, percentages will be based on the total number of subjects in the corresponding dose group.

Continuous data will be summarized using descriptive statistics (N, mean, standard deviation, median, minimum and maximum).

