**Table 2 Imputation rules for an incomplete or missing AE date**

Field	Incomplete date	Missing date
AE resolution date	The upper limit.	No imputation; the AE is considered as ongoing.
AE onset date	No imputation.	No imputation.

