### **13.7 Handling of missing/incomplete date and time fields**

This section describes some general principles to be followed in the case of missing or incomplete date/time.

Missing or incomplete dates are handled as follows:

- Dates are split into 3 parts: year, month and day. Year is the top-level, month is medium level and day is low level. If a part that is expected to contain a number is numeric but the value is outside a valid range, the complete date is handled as missing. For example, if date = 44Nov2000 the whole date is considered to be missing.
- If a part that is expected to contain a number is not numeric, i.e., contains values such as ND, NA, --, ??, 2?, that part is considered to be missing.

- If a part is missing, all lower level parts are considered to be missing. This means that a ddmmy date '21ND99' is considered as '----99'.
- If year is missing, then whole date is considered to be missing, unless reasonable assumptions support an imputation (imputation rule and rationale for assumption will be provided).

Imputation of missing or incomplete dates/times are further specified in the associated analysis section. Unless noted otherwise, the non-imputed date/time will be reported in listings.

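### AEs without a complete onset date are left out of every by-dose treatment-emergent table, even when only one treatment period fits

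*SAP*

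**What the plan says.** Protocol 10.2.4.1 leaves the handling of missing or incomplete AE dates to the SAP. Protocol 10.3.5 assigns events within a treatment period to the dose taken in that period, and Protocol 10.3.5.2 plans tables of TEAEs and SAEs by dose.

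The SAP fills this in as follows.

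- SAP 10.1 on dose: "AEs will be assigned to the dose group based on the AE start date".
- SAP 10.1 on partial dates: "AEs with an incomplete or missing start date will not be assigned to a treatment period".
- SAP 10.1 on treatment emergence: "Treatment-emergent AEs are those that occurred from the start of the treatment period", with the window closing 5 days after the last intake of that period, or at the start of the next period if earlier.
- SAP 10.1 also says "An incomplete (day or month missing) or missing AE date will be imputed as described in the" table that follows. That table, Table 2, imputes only an incomplete resolution date. Its onset row reads "AE onset date No imputation. No imputation".
- SAP 13.2 on treatment periods: "These treatment periods are used to assign assessments/events to dose groups (including single-blind placebo").
- SAP 13.7, the general date section, only refers back: "Imputation of missing or incomplete dates/times are further specified in the associated analysis section".
- SAP 4 on presentation: "Unless noted otherwise, all statistical summaries will be presented by dose group and in the following order".

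**The concern.** The rule acts on the one date that decides both whether an AE is treatment-emergent and which dose it belongs to. Without that date the event is neither imputed nor assigned. For treatment-emergent counts the rule can therefore take events away and never add them. It also does so when the recorded information is enough to identify the dose.

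Protocol 1.3.1 makes safety data, together with WASO, part of the basis for the dose taken into later trials. The by-dose AE tables are where a reader looks first. With about 50 subjects per dose, one missing subject changes a row visibly. SAEs, related AEs and AESIs have no rule of their own for partial onset dates, so they follow the same one.

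**Working it through.** The plan states no figure on this point. The check traces the rule and then does calendar arithmetic.

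**Tracing an event with an incomplete onset date**

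1. SAP 10.1 gives it no treatment period, and Table 2 imputes no onset.
2. SAP 13.7 adds no fallback.
3. Treatment emergence is defined by period dates, so the event cannot be classed as treatment-emergent.
4. The non-treatment-emergent and post-treatment classes in SAP 10.1 are also defined by period dates, so neither clearly catches it.
5. SAP 13.2 makes the treatment period the general route to a dose group, so the event has no column in a by-dose table. SAP 10.1 names no pooled AE table.
6. There is one exception. Deaths are assigned to the last dose before death, and AEs leading to discontinuation or interruption to the last dose before onset. A death with a known date therefore still reaches a dose group. For the AEs, the rule still needs to know when onset occurred.

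**How much a partial date can tell**

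Inputs: 2 dosing nights per period and a 5- to 12-day washout (Protocol 3.1.1.2).

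- Cycle length: 2 + 5 = 7 days, up to 2 + 12 = 14 days. As a check, 5 × 2 + 4 × 5 = 30 days and 5 × 2 + 4 × 12 = 58 days, which agrees with Protocol 3.1.2.
- Treatment-emergent window: from the first dose day to 5 days after the second intake, which is 7 calendar days. That is 7/7 = 100% of the shortest cycle and 7/14 = 50% of the longest.
- Suppose only month and year are known, and the month lies wholly inside the five cycles. It then touches 4 to 5 periods with a 7-day cycle and 2 to 4 with a 14-day cycle. If onset is assumed uniform over that month, the chance that it was treatment-emergent is 100% with a 7-day cycle and about 45% to 55% with a 14-day cycle.
- At the edges of the treatment phase, or when a resolution date is known, only one period may fit.

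**Two illustrations with assumed dates**

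- Period 1 doses are taken on 31 March and 1 April. The next period starts no earlier than 31 March + 7 days = 7 April, and the treatment-emergent window runs to 1 April + 5 days = 6 April. An AE has onset recorded as April with no day, and resolved on 5 April. Onset lies between 1 and 5 April, so it is certainly in period 1 and certainly treatment-emergent. The SAP still drops it.
- Period 5 doses are taken on 25 and 26 April. By SAP 13.2 the period ends no later than 26 April + 12 days = 8 May. An onset recorded as May fits period 5 or the time after it, and no other period. Here only 1 May lies inside the treatment-emergent window (26 April + 5 days).

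**Size per event**

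One subject lost from a row is 1/50 = 2.0 percentage points. With 10% dropout (Protocol 3.1), 50 × 0.9 = 45, and 1/45 = 2.2 points.

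**The case against.** The strongest reply is that very few events will be affected. AEs are collected each evening and morning at PSG visits and at a call after the end of treatment (Protocol 7.2 and Table 3). All dosing takes place at the centre. Data queries continue until database closure (Protocol 11.3), and SAEs must be reported within 24 hours of first knowledge (Protocol 9.2.5). The documents give no rate of partial onset dates, and the 2-point figure shows what one lost subject is worth, not that one will be lost. All of this stands.

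A reader might infer that a serious event could disappear from the report. The documents do not support that. All AEs are listed, SAEs and AESIs also have their own listings, and deaths have the last-dose rule. What is wrong is the tabulated incidence, not the visibility of the event.

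A reader might also infer that the rule flatters the drug. That is not shown. Events in placebo periods are dropped as well, which on its own would widen the apparent difference between drug and placebo. No differential loss by dose is demonstrated. The safety example that Protocol 1.3.1 names for dose choice is next-day residual effect. DSST, KSS and observed sleepiness are taken on scheduled mornings and do not depend on AE onset dates.

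Nor can it be said that a month-and-year date always covers several periods. Edge months and known resolution dates can leave only one. That limits the claim of ambiguity, but it strengthens the case against dropping the event.

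Finally, declining to guess a dose is defensible in a dose-finding crossover. Giving ambiguous events to the highest compatible dose would build in a gradient. Each dose occurs once per period in the Latin square, so any k periods contain 50 mg in k of the 5 sequences: 40%, 80% and 100% for k = 2, 4 and 5. This argues against guessing. It does not justify dropping an event whose dose is known, or leaving ambiguous events out of the tables altogether.

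**Conclusion.** The point holds as a minor reporting defect. Under SAP 10.1 and Table 2, an AE without a complete onset date is absent from all by-dose treatment-emergent AE, SAE and related-AE tables. This is so even where its dates are compatible with only one period. The exclusion from those tables is not written out in the SAP, but it follows from the assignment rule, the definition of treatment emergence and SAP 13.2.

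Absolute incidence can only be understated, by about 2 percentage points per lost subject on the assumption of 50 subjects per dose. The total effect is unknown, probably small and possibly zero. Its direction for contrasts between doses, or with placebo, cannot be determined from the documents.

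**What to change.** Amend SAP 10.1 and Table 2, before treatment codes are released for analysis, along these lines:

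1. Count an AE as treatment-emergent unless its partial onset date or its resolution date rules this out.
2. If only one treatment period is compatible with those dates, assign the event to the dose of that period. Include the single-blind run-in among the periods considered, because SAP 13.2 treats it as a dose group.
3. If several periods are compatible, do not guess. Show the event in a column for dose not assignable.
4. Add an all-subjects column to the AE tables so that totals reconcile with the listings.

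The logic is already in the SAP: section 6.4.3 uses the earliest and latest possible dates to classify concomitant therapies with partial dates.

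The cost is a paragraph of text and minor programming. The downside is that a few events that were not truly treatment-emergent may be counted as such. The May example above could be one, since only one day of that month lies inside the window. A footnote giving the number of events classified by this rule would let readers judge its influence.
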